# End of treatment questionnaire

# - Young People

After their final session, YP will complete end of treatment questionnaires which will measure engagement with the intervention via self-report, website acceptability, preference for mode of delivery and any barriers to treatment. These will be distributed by an unblinded member of the research team. Young people who withdraw from the intervention before their 8th session will be asked to complete this measure at the point they stop their BA sessions. The questionnaire will generate quantitative and qualitative data which will contribute to overall acceptability measures.

#### - Therapists

BA therapists will complete bespoke questionnaires when they have completed delivering all therapy sessions. End of treatment questionnaires will address acceptability of the intervention, acceptability of using a digital platform, preferences for mode of delivery, and any barriers faced during treatment. End of treatment questionnaires will be distributed by an unblinded member of the research team and will generate a combination of quantitative and qualitative data, which will contribute to overall acceptability measures of the intervention.

## BA Completion Form (Discharge Information)

The therapist will also be asked to complete information about discharge and any further treatment offered to the young person following completion of behavioural activation. The form will capture information about how many sessions were delivered, and the reasons for delivering more or less than the planned 8 if applicable.

# Patient Health Questionnaire (PHQ-9)

The PHQ-9 is a self-administered patient questionnaire used to monitor the severity of depression, which scores each of the nine DSM-IV criteria for depression as "0" (not at all) to "3" (nearly every day) (Kroenke, Spitzer and Williams, 2001). This will be completed by the parent/carer to report their own mental health.

# Generalised Anxiety Disorder (GAD-7)

The GAD-7 is a seven item instrument that is used as a severity measure for generalised anxiety disorder (GAD) (Spitzer er al., 2006). Each item asks the individual to rate the severity of his or her symptoms over the past two weeks as 'not at all', 'several days', 'more than half the days', and 'nearly every day', respectively. This will be completed by the parent/carer to report their own mental health.

# Session log for BA

BA therapists will be asked to complete a session log after each BA session they have delivered. Session logs will identify whether the session was recorded, whether the session was in-person or remote, who was present in the room and any problems encountered during the session. Session logs will be used to monitor intervention delivery by the Trial Managers and support the statistical analysis.

## Serious Adverse Event Forms

Adverse event forms will be completed by a trial manager when they have been reported. Adverse event forms will detail what the event was, who reported it and the outcomes. The procedure for reporting and collecting data about adverse events is highlighted in Section 7.6

# Fidelity to BA rating scale

Where consent has been provided from the participant, BA therapy sessions will be audio recorded. To assess the fidelity of the BA component, fidelity to BA principles will be assessed via the review of therapy recordings against the fidelity criteria by a clinician who has expertise in BA and who is external to the delivery of BA in the BAY trial. This procedure will occur once the last recruited participant has attended their final session. 10% of BA session recordings will be assessed and selected at random and a procedural fidelity checklist completed by the assessor whilst listening to the audio recording of the sessions.

## **Qualitative interviews**

Refer to the Section 10: Qualitative Study for further details.

# 4. STUDY DESIGN

We will conduct a parallel two-group RCT, with an internal 8-month pilot to compare the effectiveness of BA +psychoeducation+TAU against TAU+psychoeducation. Nested within the study will be an embedded qualitative study to assess acceptability and implementation of behavioural activation, and economic evaluation (as described in section 10 & 11) of BA's cost-effectiveness relative to psychoeducation+TAU alone.

## 5. STUDY SETTINGS

The study will be conducted within CAMHS sites responsible for providing support to young people with moderate and severe depression. These sites will be involved in the identification of study participants and will be the locations for intervention delivery. The site must have a BAY trained therapist (trained by psychology leads based within each Trust, PI and psychologist PI from the study) and local supervisor to deliver the BA component. To allow for the option of remote delivery of BA, the site must also have access to the required software and technology to be able to deliver the BA sessions using

video conferencing software. Each CAMHS site will also provide treatment as usual for each participant, which will include access to any urgent care that may be required.

Research Assistants will be based either within CAMHS or their R&D unit within the NHS Trust, and they will be responsible for recruitment and data collection at all timepoints. Some measures will be collected by the trial managers to avoid unblinding the RAs.

#### 6. PARTICIPANT ELIGIBILITY CRITERIA

#### 6.1. Inclusion criteria

Young people will be eligible for the study if they:

- 1. Are aged 11-17 years at the date of consent.\*
- 2. Score ≥27 on the Mood and Feelings Questionnaire (this is the standardised cut-off by which elevated symptoms of depression warrant further assessment and potential intervention).
- 3. Recently accepted into specialist CAMHS. (≤6 weeks)
- 4. Provide consent, or assent along with their carer's consent (if applicable), to participate in the study

\*Up to 17 years and 6 months

#### 6.2. Exclusion criteria

Young people will not be eligible for the study if they:

- 1. Have a severe mental illness that is not primarily depressive (e.g. schizophrenia, non-depressive psychosis, current mania, anorexia).
- 2. Are at a high risk of imminent suicide or presenting with a high frequency of severe self-harm and therefore need a different pathway of care and support (clinical judgement).
- 3. Cannot speak English to a sufficient level to understand the intervention and research materials.
- 4. Have an intellectual disability of a level which prevents adequate understanding of the study or intervention materials.
- 5. Have received 8 sessions of therapist-led CBT (including behavioural activation) in the previous 6 months.

6. If there is more than one eligible child in the family, only one child will be consented into the study and randomised and the same randomised treatment will be offered to the sibling.\*

\*This is applicable to a young person who has a sibling already consented into the study (regardless of whether the sibling is being actively followed-up), and if two or more siblings are assessed and accepted into CAMHS at the same time.

#### 7. STUDY PROCEDURES

#### 7.1. Recruitment

We will recruit participants through NHS CAMHS. CAMHS sites within 5 NHS Trusts will be invited to both promote the RCT and assist with identifying young people who may be suitable and interested in participating. BAY research team members will work closely with members of the CAMHS team to ensure that the professionals understand the study and its inclusion criteria. The study will be embedded within the CAMHS team to ensure all potential participants are aware of the opportunity. There will be 3 methods of recruitment through the CAMHS service: 1) Identification by clinician, 2) MDT Meetings, and 3) Screening records

# 1) Identification by clinician

CAMHS clinicians conducting referral assessments will be provided with an information leaflet about the trial and the inclusion criteria, as well as multiple study information packs prepared by the research team to distribute to potential participants. They will be asked to consider potential participants for the trial when conducting referral assessments.

If considered by the clinician to potentially be eligible for the trial, the clinician will briefly discuss the trial with the participant. If they are interested and with their permission, the clinician will use the eligibility screening criteria pro-forma to determine whether they are potentially eligible. The MFQ may have been conducted via routine clinical assessment and this score be used by the clinician to help determine potential eligibility. If the young person seems potentially eligible as a result of clinician screening,, they will be provided with a study information pack by the clinician. This will include participant information sheets (ones for young people and ones for parents/guardians (as appropriate)). Having read the study information, if a young person is interested in taking part in the research, the clinician will email (via secure NHS email) their contact details and name (with the participants verbal consent) to the researcher. The researcher will telephone potentially eligible participants to discuss the study with them and answer any questions.

## 2) MDT Meetings attended by the RA

After CAMHS have conducted an initial assessment with the young person, an MDT meeting is held to confirm the young person's acceptance into specialist CAMHS due to low mood. RAs will attend this meeting on a regular basis to identify potentially eligible participants for the study. An invitation letter from the CAMHS clinician and study information pack will be sent to the family including a copy of the Participant Information Sheet by a CAMHS clinician/team member. The participant is asked to call or email the RA if they are interested in the study or have any questions. If the RA does not hear back within 7 days of sending out the study information, they contact the family via telephone and/or email to see if they are interested in the study and follow the eligibility screening process specified below.

# 3) Screening records by the RA

As the RA will be employed by the relevant NHS Trust, they will be provided with access to the patient records of the CAMHS service involved in the study. On a regular basis, the RA will screen the records to identify newly accepted young people with low mood who are potentially eligible young people. Search terms for screening patient records will be standardised across CAMHS sites. An invitation letter from the CAMHS clinician and study information pack will be sent to the family including a copy of the Participant Information Sheet by a CAMHS clinician/team member. The participant is asked to call or email the RA if they are interested in the study or have any questions. If the RA does not hear back within 7 days of sending out the study information, they will contact the family via telephone and/or email to see if they are interested in the study and follow the eligibility screening process specified below.

#### Eligibility screening process

Once a YP has been identified as being potentially eligible from clinician screening, a MDT or records, and the family have received the study information pack as highlighted above, the RA will contact the YP if 16 or over, or the carer if under 16, introduce the study, and, with their written agreement, determine whether a young person is eligible for participation by asking the young person to complete the MFQ and completing a screening checklist. Anyone attaining a score of  $\geq$ 27 on the MFQ will be eligible for study entry (if they also satisfy the other inclusion criteria).

The researcher will then arrange a suitable time to meet to complete the consent form and conduct the MFQ at baseline. Those with a score  $\geq$ 27 MFQ will go on to complete the full baseline assessment. Those who do not meet the threshold will not be recruited on to the study and will continue to receive treatment as usual (this will be explained to the participant prior to giving consent).

If an eligible YP declines to participate, they will be asked verbally their reason for this and the research assistant will complete a pro-forma based on their response.

[figure not shown]
Baseline assessments will be offered face-to-face at CAMHS, NHS or affiliated University sites, in the family home, via video conferencing or another suitable location at a mutually agreed time and date with the young person and parent/guardian; however, these assessments can take place virtually if this is preferred by the YP. All baseline visits will

be arranged ensuring that participants (and parent/guardians) have had at least 24 hours to decide whether to take part in the research after receiving study information.

[figure not shown]
The study information that potential participants will receive includes:

- Invitation letter;
- Participant Information Sheet, including a step-by-step guide for how to participate and what is involved, together with the researchers contact details;
- Consent/Assent form.

Flow Diagram 1. Participant identification and Recruitment-Route 1

A member of the research team informs the participant (and their carer, if applicable) the BAY therapist if randomised to receive BA (and their clinical supervisor), the CAMHS service if TAU and informs the participants GP via letter of the randomisation outcome.

A member of the research team informs the participant (and their carer, if applicable) the BAY therapist if randomised to receive BA (and their clinical supervisor), the CAMHS service if TAU and informs the participants GP via letter of the randomisation outcome.

#### 7.2. Informed consent

Prior to the baseline visit the researcher will call the carer and/or young person to reiterate the trial aims, discuss what participation entails and answer any questions young people and/or their carers have regarding the research. If happy to proceed, informed consent/assent will be obtained from young people and carers. Throughout the trial, potential participants who decline to take part in the trial will be asked verbally by the researcher their reason for not taking part. The researcher will record this on a 'tick box' pro-forma with a list of potential reasons for declining, with an 'other' option and free text option. Potential reasons for refusal will be discussed with our advisory panels and will inform the main trial process.

Throughout the recruitment process the research assistant will attempt to contact the participant no more than four times.

Consent will be obtained on paper or via a secure online data capture system, where participants will be sent the link via email by the researcher and asked to tick all clauses that apply and then provide an electronic signature. Participants can complete the consent form independently before the baseline MFQ, or at the baseline appointment with the researcher. The consent process will vary depending upon the age of the young person.

# Young people aged 11 to 15 years

Young people aged 11 to 15 years will be required to complete an assent form, alongside their carers consenting for them to be able to take part in the trial. The research assistant, with guidance if necessary from the clinician or PI at the local CAMHS site, will determine the participant's capacity to provide informed consent/assent (the YP can understand the information given to them about the study, retain the information, be able to relay the information back to the research assistant and can make a decision about participation). Training will be provided to RAs regarding assessing competence/capacity. As part of this, a carer will be required to confirm that they will support their child during their time in the trial. The carer will sign a consent form on the young person's behalf, including permission for their child to take part in the study as well as consent for themselves to take part in the study.

## Young people aged 16 to 17 years

Young people aged 16 to 17 years will be required to complete a consent form to participate in the trial. Whilst carer consent will not be required, young people will be reminded that involving carers in the completion of BA may provide a useful form of additional support during their participation (e.g. in supporting activation attempts). Whether 16- to 17-year-old participants choose to involve carers in the completion of BA is based upon individual choice. 16-17 year olds will be informed that their parents will be asked to complete their own questionnaires if they choose for them to be involved in the study via the Participant Information Sheet and if in agreement the parent/carer will sign their own consent form.

#### 7.3. Procedure

Following informed consent/assent the young person will be assigned a participant number and will be asked to complete a series of standardised measures with a trained researcher captured on paper or electronically using REDCap (Research Electronic Data Capture).

The young person will conduct the MFQ at baseline with the researcher. Those with a score ≥27 MFQ will go on to complete the full baseline assessment. Those who do not meet the threshold will not be recruited on to the study and will continue to receive treatment as usual (this will be explained to the participant prior to giving consent).

The full baseline assessment will include: demographic questionnaire, DAWBA, SDQ, RCADS, WAI-S, CHUD-9D, EQ-5D-Y, WHO scale, suicidality questions, service use, GBO.

The carer will complete: MFQ, DAWBA, SDQ, and EQ-5D-5L on behalf of their child's mental health and PHQ and GAD-7 to report their own mental health.

On completion of the baseline measures, participants will be randomised to either receive BA+PE+treatment as usual or treatment as usual +PE.

A member of the trial management research team will inform the participant (and their carer, if applicable) and the BAY therapist if randomised to receive BA (and their clinical supervisor) and inform the participants GP via letter of the randomisation outcome. Upon informing the participant of their allocation, the trial managers will distribute the psychoeducation leaflet to the participants.

If randomised to BA, treatment sessions will be arranged by the local BA therapist who will liaise with the young person and, if appropriate, their carer (e.g for children aged between 11-15 years). Trial Managers will distribute a session log for the BA therapist to complete online/ on paper upon completion of each BA session delivered. Session logs will collect information about whether the session was recorded, whether the session was in-person or remote, who was present in the room and any problems encountered during the session.

If randomised to TAU+PE alone, the local manager will arrange treatment as usual as required. The researcher will arrange follow-up meetings at 12 weeks, 6 months and 12 months from the point of randomisation and will keep in contact with the young person before these meetings as needed. Participants will only be asked to complete the 12 month follow-up if they are recruited before July 2024 due to the study completion date (August 25).

Research assistants will screen clinical records at the end of the young person's participation to identify what other treatment and therapies they have been receiving from CAMHS. If there is any information about private care this will be noted too. Research assistants will use a treatment as usual questionnaire to record this information. This is a list of therapies and interventions offered by CAMHS, gathered from PPI panels and PIs at each site, an option for 'other' and discharge information.

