# **STUDY SUMMARY**

Study title	Rohavioural Activation for Vo	ung poople with depression in			
Study title	Behavioural Activation for Young people with depression in specialist child and adolescent mental health services				
Short title	BAY: Randomised Controlled Trial				
Study design	Randomised Controlled Trial with internal pilot				
Participants	Young people aged 11 to 17 y	ears with moderate to severe			
	depression				
Planned sample	446 young people				
size	51 . 14				
Treatment	Behavioural Activation will be				
duration	sessions +Treatment as Usual				
Follow-up duration	12 weeks, 6 months, and 12 m (naturalistic follow up at 12 m	•			
Planned study	4 years (45 months)	ionuisj			
period	Tycais (45 monuis)				
periou	Objectives	Outcome Measures & Data			
		Collection Tools			
Primary	Estimate the clinical and	Primary outcome measure			
	cost effectiveness of BA +	(primary endpoint 6-months			
	psychoeducation (PE) +	post-randomisation) : Mood			
	treatment as usual (TAU) on	and Feelings Questionnaire			
	depressive symptoms	(MFQ-C young person self-rated)			
	compared to PE+TAU at 6				
	months post-randomisation   Additional measures:				
	Vouth, DAMIDA Chasalina and-				
	Youth: DAWBA (baseline only), SDQ, RCADS, BADS, self-harm				
		and suicidality questions, goal-			
	based outcomes, CHU-9D, EQ-				
	5D-Y, Healthcare service use				
	schedule, Aspects of Care				
	checklist, WAI-S				
		Clinician: Session logs, End of			
		Treatment questionnaire,			
		adverse & serious adverse			
		events			
		Carer: DAWBA (baseline only),			
		MFQ, SDQ, , Carer EQ-5D-5L-			
	Childs mental health				
		PHQ-9, GAD-7- Carers mental			
		health			
		nearm			
		RA completed: Treatment as			
		usual form. Numbers discharged			
		RA completed: Treatment as usual form. Numbers discharged			

		from CAMHS; n needing therapy; (treatment as usual questionnaire & end of treatment questionnaire) Adverse & Serious Adverse Events		
Secondary	Co-design and develop our website with YP, to enhance the acceptability and effectiveness of remote delivery, and train therapists to deliver blended BA.	Feedback from young people and clinicians during development and training.		
	Conduct an internal pilot to assess recruitment and acceptability in all sites.	Progression criteria to a full trial. Collect reasons for declining. Interview participants who initially consent and then refuse to take part (early exit participants, n=15)		

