# **EQ-5D-5L**

This will be completed by carers, in relation to their own health. The EQ-5D-5L consists of 5 dimensions of health: mobility, self-care, usual activities, pain, anxiety/depression. Each dimension has 5 levels: no problems, slight problems, moderate problems, severe problems and extreme problems (EURO-QOL Research Group, 2018). Each profile of responses will be converted into its respective utility value according to the method recommended by NICE at the time the analysis is conducted.

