# 11.1 Cost-Utility & Cost-Effectiveness: trial-based analysis

The cost to train the BAY therapists and the cost of their time to deliver the intervention therapy sessions will be estimated as the intervention cost. This will be added to the cost of health and social care resources used by YP in the intervention arm to generate an overall cost for that treatment group. For the TAU+PE group, their overall cost will be generated from their use of health and social resources only. The primary analysis will take the health and social care perspective and so will only include these costs. A secondary analysis will include the cost of 'lost productivity' for parents/carers during the time they spend with YP at (and travelling to) healthcare contacts. Unit costs will be derived from published sources (e.g. NHS Schedule of Reference Costs; PSSRU Unit Costs of Health and Social Care) using the most up-to-date versions at the time of the analysis.

The measure of health benefit in the primary analysis will be YP's QALYs derived from the CHU-9D at baseline and 6-month follow-up. A secondary analysis will derive YP's QALYs from the EQ-5D-Y at these timepoints. QALYs will be estimated using an area under the curve approach.

The difference in costs between the treatment groups will be calculated using a glm regression model with log link and gamma family to account for the typically skewed nature of cost data. The difference in QALYs between the groups will be estimated using a linear regression model. Both regression models will include key covariates, as specified in the statistical analysis. An incremental cost-effectiveness ratio (ICER) will be calculated by dividing the difference in costs by the difference in QALYs between the treatment groups. This will be reported as a cost per QALY. Non-parametric bootstrapping will be used to produce a cost-effectiveness plane to demonstrate uncertainty in the results. A cost-effectiveness acceptability curve (CEAC) will also be generated to illustrate the probability that either treatment is cost-effective at a range of willingness to pay (WTP) thresholds.

The health utility of parents/carers during the study period will be derived from the EQ-5D-5L and compared between the treatment groups.

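### Section 7.3 has carers rate the child on the EQ-5D-5L, but section 3.3.1 and the carer-utility comparison in section 11.1 need carers to rate themselves

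*Protocol*

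**What the plan says.** Four places in the Protocol bear on the subject of the carer EQ-5D-5L, and a fifth gives its schedule.

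- **Section 7.3 (Procedure)**, on what the carer fills in at baseline, after three other instruments: "EQ-5D-5L on behalf of their child's mental health and PHQ and GAD-7 to report their own mental health". The sentence sorts the carer's instruments by whose health is rated and puts the EQ-5D-5L on the child's side.
- **Study summary**, carer measures: "MFQ, SDQ, , Carer EQ-5D-5L" leads into the label "Childs mental health", after which the PHQ-9 and GAD-7 carry a separate label for the carer's mental health.
- **Section 3.3.1 (EQ-5D-5L)**: "This will be completed by carers, in relation to their own health".
- **Section 11.1**: "The health utility of parents/carers during the study period will be derived from the EQ-5D-5L and compared between the treatment groups".
- **Table 1** lists a carer EQ-5D-5L at baseline and 6 months. The row does not say whose health is rated.

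For the young person's own health benefit, section 11.1 uses other instruments: "The measure of health benefit in the primary analysis will be YP's QALYs derived from the CHU-9D at baseline and 6-month follow-up". A secondary analysis uses the EQ-5D-Y.

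**The concern.** A respondent can answer an EQ-5D-5L about themselves or, as a proxy, about someone else. The two sets of answers are different measurements. Section 7.3 asks for the second at baseline, while sections 3.3.1 and 11.1 ask for the first. Staff cannot follow both.

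At stake is the between-arm comparison of carer health utility in section 11.1. BA is delivered to the young person, so a proxy rating of the young person lies much closer to the treatment than a self-rating by the carer. If proxy answers were analysed as carer utility, the result would not describe the carer's health. A later analysis plan cannot put this right, because whose health was rated is fixed when the form is completed, and the Protocol describes no data item that records it.

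**Working it through.** No power, sample size or error-rate figure is involved, so the check sets the passages side by side.

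**1. Is the conflict in the current text?** Yes. The section 7.3 sentence is complete and unambiguous. The summary table is broken in the available text, so its grouping alone would be weak evidence, but it agrees with the intact sentence in section 7.3. The conflict therefore does not come from text extraction, nor from an amendment log.

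**2. Which reading does the rest of the document support?**

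| Place | Whose health | Strength |
|---|---|---|
| Section 7.3 | Child | Explicit; baseline only |
| Study summary | Child, apparently | Synopsis, layout damaged |
| Section 3.3.1 | Carer | Explicit; the instrument's definition |
| Section 11.1 | Carer, by implication | The only planned use of the data |
| Table 1 | Carer, by implication | Label and schedule |

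Table 1 helps more than its silence suggests. It marks the proxy SDQ and MFQ as parent versions and schedules them at baseline, 12 weeks, 6 months and 12 months. The carer EQ-5D-5L has no such mark and is scheduled at baseline and 6 months only, like the PHQ-9 and GAD-7, which are carer self-reports. A proxy EQ-5D-5L would also have no use in the plan, since the young person's utility comes from the CHU-9D and the EQ-5D-Y. The weight of the document is for self-rating, and section 7.3 and the summary are the text to change.

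**3. What follows under each possible practice?**

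- Self-rating at both time points: the comparison is sound, and only the wording is wrong.
- Child rated at baseline, carer at 6 months: the 6-month values are carer utilities, but any baseline adjustment, change score or summary over the study period would combine two people's health.
- Child rated at both: the comparison is not of carer utility at all.
- Practice differing between staff or sites: the comparison is a mixture with unknown weights.

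**4. How many forms could be involved?** Only a ceiling can be given. With 446 participants there are at most 446 carer forms at baseline. If carers were retained at the 70% that section 9.1 assumes for the trial, there would be 0.70 × 446 ≈ 312 at 6 months. Both are upper limits on forms collected, because section 7.2 makes carer involvement optional for 16- to 17-year-olds. The number answered about the child could be zero.

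**5. What else is wrong in the same part of section 7.3?** The young person's baseline list departs from Table 1 in three ways. It omits the BADS, which Table 1 schedules at baseline. It includes the WAI-S, which Table 1 collects halfway through the intervention and which rates a BA therapist whom the participant has not yet met. It also names a WHO scale that is described nowhere else. These are separate list errors and do not bear on the carer-utility comparison.

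**The case against.** The strongest reply is that the document largely settles the matter itself. The instrument's own definition is explicit, the only planned analysis needs self-ratings, and Table 1 schedules the form with the carer self-reports. On that view section 7.3 is a drafting slip. Carers answer the instruction printed on the questionnaire, not a sentence in the Protocol, and the form in use may well be correct. Section 7.3 also covers baseline only, and nothing gives the same instruction for 6 months.

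Most of this stands and limits the point. It does not remove it. Section 7.3 is the text that describes the baseline visit, and following it as written would supply the wrong input to a pre-specified comparison. The form is not in the document, so the benign reading needs a check.

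Two stronger readings are tempting. A reader might infer that carers have in fact been answering about the child, so that a benefit to the young person will be reported as a spill-over benefit to carers. The document does not show this: it has no completed forms, gives no basis for assuming any particular share of proxy answers, and speaks only of comparing carer utility between the groups. A reader might also infer that the cost-effectiveness result is compromised. It is not, because the QALYs in that ratio come from the young person's own instruments.

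**Conclusion.** The contradiction is real and should be corrected. Its reach is one secondary economic comparison, that of parent and carer health utility between arms. The MFQ-C primary outcome, the CHU-9D and EQ-5D-Y QALYs and the cost-effectiveness ratio are unaffected. The size of any distortion cannot be estimated: it depends on the printed instruction and on site practice, neither of which the Protocol shows, and it may be nil. The conclusion assumes only that section 11.1 means the carer's own utility, which is how it reads and what section 3.3.1 says.

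**What to change.** 1. Amend section 7.3 and the study summary to say that the carer EQ-5D-5L concerns the carer's own health, in line with section 3.3.1, section 11.1 and the Table 1 schedule.
2. Check the instruction printed on the form in use at baseline and at 6 months, and any site instruction to research assistants.
3. If a form or site instruction asked about the child, do not report those data as carer utility, and report the number affected by arm.
4. As a separate minor correction, align the young person's baseline list in section 7.3 with Table 1: add the BADS, remove the WAI-S, and remove or define the WHO scale.

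The wording changes and the form check cost little. The possible loss comes in step 3. With no recorded item to separate proxy from self-rated forms, exclusion may have to be by form version, site or time point. If the printed form itself asked about the child, the carer-utility comparison may not be possible.
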